Following enrollment, baseline data and selected outcome markers will be assessed. Then all patients will undergo a 4-week care optimization phase during which time we will review the patient's dialysis care and make adjustments (if necessary) to meet standard of care guidelines as defined by CMS, KDOQI and KDIGO (Table 1). Outcome markers will be reassessed again after completion of the 4-week care optimization phase. At this time all patients will also undergo a baseline exercise test to measure peak VO₂ and a DXA scan for body composition analysis before starting EMS training.

| Table 1 | |
|---------------------------|--|
| Parameter | Optimized care goals |
| Vascular access | Discontinuation of central venous catheter and use of arteriovenous access |
| Fluid removal | Optimize dry weight. Limit UF rate to ≤ 13 ml/kg/hr |
| Solute removal | Minimum dialysis time ≥ 3.5 hours. Goal 4 hours. kT/V ≥ 1.4 |
| Acid-base | Pre-dialysis HCO ₃ between 22-27 mEq/L |
| Anemia | Hemoglobin 9.5-11 g/L, if on erythropoietin; Iron saturation $\geq 20\%$ |
| Ca, PO ₄ , PTH | Calcium, PO ₄ within normal levels; PTH ≤ 600 pg/ml |

EMS training will be done while the patient is on hemodialysis. At the first EMS training session, optimal EMS settings will be established and patients will be taught how to apply the electrodes and use the muscle stimulator. For patients who agree we will also do a muscle biopsy of the quadriceps (vastus lateralis) muscle at this first training visit before starting EMS training. Patients will be seen at the next dialysis session and again after 7 days to confirm that they are doing the EMS training properly. Patients are then seen at Day 14, 28, 42, 56, 84 and 112 after starting EMS training to assess for any adverse events, monitor progress with EMS training and adjust the EMS settings to make sure they are at the optimal tolerated intensity of muscle stimulation. The EMS training will continue for 16 weeks. At Day 56 and Day 112 (8 and 16 weeks) of EMS-training all the primary and secondary outcome variables including exercise stress test for peak VO₂ and DXA scan will be performed. For patients who agree we will also perform a muscle biopsy at a dialysis visit around Day 56 and Day 112 (not the same day as the exercise stress test). One month after stopping EMS training the patient will be seen and the outcome variables will be repeated except for the DXA scan and the exercise stress test.

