treatment and after 8 and 16 weeks of EMS training to determine the chronic effect of EMS training on muscle gene expression. Gene expression analysis will be done using Affymetrix Human Exon 1.0 ST arrays as previously described.⁷⁰ We will first examine specific genes that are highly overexpressed or under-expressed after acute and chronic exercise compared to the baseline (pre-EMS). We will also look for biological pathways activated or suppressed by acute and chronic exercise specifically looking at pathways relating to muscle glucose metabolism and insulin response, mitochondrial biogenesis and function, muscle phenotype, growth and energy metabolism, oxidant stress and inflammation. A future goal of this research is to compare the gene expression response to EMS in this study with that seen in patients with normal renal function and varying levels of CKD to see if the gene response profile is qualitatively different in patients with varying levels of kidney function. We are also interested how the gene expression profiles seen with EMS compare to that seen with traditional volitional aerobic exercise to determine if EMS activates different genes or biological pathways than volitional exercise.

5. Visits & Assessments.

Patients will be identified from the population of patients on regular maintenance hemodialysis at one of the University of Iowa dialysis units. Potential subjects will be approached at a dialysis visit and informed of the study.

5.1. Visit 1. If they indicate an interest in participating we will proceed with obtaining written informed consent and confirm that they meet all the inclusion criteria and none of the exclusion criteria.

- Obtain informed consent to participate and consent to access additional appropriate medical records
- Review inclusion and exclusion criteria

Baseline data collection (Day -35 to -28). Performed at dialysis unit or CRU as appropriate. Up to 4 hours time.

- Record demographics and baseline disease characteristics
- Record past medical history and current review of symptoms
- Record current dialysis orders
- Record episodes of dialysis hypotension (SBP<90 or symptoms needing saline, last 6 HD sessions)
- Record baseline exercise status (minutes of exercise per week)
- Record concomitant medications
- Malnutrition-inflammation (MIS) assessment
- Kidney Disease Quality of Life-36 (KDQOL-36) assessment
- Patient Health Questionnaire-9 (PHQ-9)
- Record sitting blood pressure and pulse

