- Physical examination by a physician
- 6-minute walk test
- Record height, weight, waist circumference, hip circumference
- Thigh circumference bilaterally
- Record most recent standard dialysis monthly lab tests.
 - o Monthly labs (predialysis): albumin, alkaline phosphatase, bicarbonate, blood urea nitrogen, calcium, chloride, complete blood count, creatinine, iron studies, ferritin, hemoglobin A1c (if available), phosphorus, potassium, sodium, total protein, 25 hydroxy vitamin D. eGFR calculation by modified MDRD equation from enzymatic creatinine determination)
 - o Monthly labs (postdialysis): blood urea nitrogen. Calculated urea reduction ratio from pre and

post dialysis BUN.

- Fasting blood sample (30 ml) for:
 - o Insulin and glucose
 - o Interleukin-6 (IL-6), tumor necrosis factor alpha (TNF α), C-reactive protein
 - o Glutathione (reduced and oxidized forms), glutathione peroxidase (GPx), superoxide dismutase (SOD), catalase (CAT), F2 isoprostane and protein thiols.
- Measure quadriceps muscle strength (bilaterally)
- 48 hour activity monitoring (using wrist watch monitor between dialysis sessions).

5.2. Visit 2. Pre-EMS training data collection (Day -7 to 0). Performed at dialysis unit or CRU where specified. Time required up to 4 hours.

- Record any new medical conditions, symptoms or complaints
- Record current dialysis orders
- Record episodes of dialysis hypotension (SBP<90 or symptoms needing saline, last 6 HD sessions)
- Record current exercise status (minutes of exercise per week)
- Record concomitant medications
- Malnutrition-inflammation (MIS) assessment
- Kidney Disease Quality of Life-36 (KDQOL-36) assessment
- Patient Health Questionnaire-9 (PHQ-9)
- Record vital sign measurements (predialysis or non-dialysis day, same timing as baseline measures)
- 6-minute walk test
- Record weight, waist circumference, hip circumference
- Thigh circumference bilaterally
- Record most recent dialysis monthly lab tests. (Drawn no more than 7 days prior to optimization visit)
 - o Monthly labs (predialysis): albumin, alkaline phosphatase, bicarbonate, blood urea nitrogen, calcium, chloride, complete blood count, creatinine, iron studies, ferritin, hemoglobin A1c (if available), phosphorus, potassium, sodium, total protein, 25 hydroxy vitamin D. eGFR calculation by modified MDRD equation from enzymatic creatinine determination)
 - o Monthly labs (postdialysis): blood urea nitrogen. Calculated urea reduction ratio from pre and post dialysis BUN.

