- Fasting blood sample (30 ml) for:
 - o Insulin and glucose
 - o Interleukin-6 (IL-6), tumor necrosis factor alpha (TNF α), C-reactive protein
 - o Glutathione (reduced and oxidized forms), glutathione peroxidase (GPx), superoxide dismutase (SOD), catalase (CAT), F2 isoprostane and protein thiols.
- Measure quadriceps muscle strength (bilaterally)
- 48 hour activity monitoring (using wrist watch monitor between dialysis sessions).
- DXA scan (performed in CRU)

- Perform exercise stress test to determine peak VO₂ (performed in CRU)

5.3 Visit 3. Initiate EMS training (Day 0). Performed in dialysis unit and CRU. 60-75 minutes. 30 minutes extra for optional muscle biopsy, if performed.

- Perform pre-EMS muscle biopsy before starting dialysis (optional)
- EMS training is done while on hemodialysis starting approximately 30 min after dialysis initiation.
 - o Record pre-EMS blood pressure and pulse
 - o Initiate EMS training on quadriceps muscle of leg not used for muscle biopsy for 15 minutes while on dialysis
 - o Measure and record BP and pulse before and just prior to completion of EMS training.
 - o Record any symptoms related to EMS
 - o Train patient how to use EMS device.

5.4 . Visits 4-8, 11. EMS training visits (Day 2/3 and 7). Performed in dialysis unit. Time required up to 45 minutes.

- Record any new medical conditions, symptoms or complaints
- Observe patient initiate and perform EMS training.
 - o Adjust stimulus intensity to maximum tolerated by patient for both legs
- Record EMS setting used.
- Record pre-dialysis sitting BP and pulse
- Record post-dialysis sitting BP and pulse

5.5 Visits 9 &12. Outcome assessment visits (Day 56 & 112 ± 7 days). Performed in dialysis unit or CRU where specified. Time required up to 4 hours.

- Record any new medical conditions, symptoms or complaints
- Record current dialysis orders
- Record episodes of dialysis hypotension (SBP<90 or symptoms needing saline, last 6 HD sessions)
- Record current exercise status (minutes of exercise per week)
- Record concomitant medications
- Malnutrition-inflammation (MIS) assessment
- Kidney Disease Quality of Life-36 (KDQOL-36) assessment
- Patient Health Questionnaire-9 (PHQ-9)
- Record vital sign measurements (predialysis or non-dialysis day, same timing as baseline measures)
- 6-minute walk test
- Record weight, waist circumference, hip circumference
- Record thigh circumference bilaterally
- Record most recent dialysis monthly lab tests.

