Potential risks seen with the exercise stress testing for VO₂ peak or EMS training are listed below along with the proposed management. All patients will have a formal exercise stress test to determine VO₂ peak in the CRU before starting EMS. A physician will be immediately available for these tests. Problems seen with exercise will be detected during that initial testing and addressed before proceeding with EMS training. The cardiopulmonary demand of EMS will be less than the maximal exercise stress test.

6.2.1. Angina or ischemic EKG changes. Exercise will be terminated and the patient monitored until the angina or EKG changes resolve. The study physician will be contacted. If the chest pain or EKG changes persist the patient will be transported to the ER for evaluation. Additional physician evaluation will be needed before the patient is allowed to continue in the study.

6.2.2. Arrhythmia. Complex arrhythmias or second or third degree heart blocks will lead to immediate termination of the exercise stress test. The study physician will be contacted. The patient will be

monitored until the arrhythmia resolves and the primary physician will be notified to follow-up on the results. Additional cardiology evaluation will be required before the patient can proceed in the study.

6.2.3. Hypertension. Systolic BP >250 mmHg or diastolic > 120 mmHg will be grounds to terminate the exercise stress test and contact the study physician. The patient will be monitored until the blood pressure returns to baseline. The patient's blood pressure management will be reviewed before proceeding into the EMS training phase of the study. An EMS session will be terminated for a systolic BP>200 or diastolic BP>110.

6.2.4. Hypotension. Systolic BP dropping more than 20 mmHg during the exercise stress test will be grounds for terminating the test. The study physician will consult with the primary care physician about further cardiology evaluation before proceeding with the EMS training. An EMS session will be terminated for a systolic BP<90.

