8. Statistical analysis/Power calculations.

This is a pilot feasibility and preliminary efficacy study to determine whether EMS can be delivered to this population and to assess the magnitude of the change and variability in the primary and secondary outcome measures. Data derived from this study will allow planning of a larger randomized controlled study. We plan to recruit up to 15 patients into the trial and complete the trial within 1 year. There will be 5 measurements of the primary and most of the secondary outcome variables in each patient. These will be performed at enrollment, after 4 weeks of "dialysis care

optimization" before starting the EMS intervention, then at 8 and 16 weeks after initiation of the EMS intervention and finally 4 weeks after stopping EMS. The DXA scan, measurement of peak VO₂ will only be performed three times (before starting EMS and then again at 8 and 16 weeks of EMS training). The optional muscle biopsy for gene expression analysis will be performed up to 4 times in patients who agree to this analysis (before and after the first EMS treatment, at 8 and 16 weeks of EMS training). Summary statistics will be used to describe and analyze the data. Changes over time in the outcome variables will be analyzed using the Friedman analysis of variance by ranks to determine if there was a statistically significant effect of EMS. A P<0.05 will be considered statistically significant. Regression analysis will be used to determine if the change in HOMA-IR or LAR is correlated with the magnitude of the observed exercise training effect (i.e. the increase in peak VO₂ or quadriceps muscle strength at 4 months) or maximum intensity of EMS stimulation used during training.

Based on an estimated baseline mean (\pm SD) HOMA-IR score of 4.8 (\pm 1.7) mg/dl· μ U/ml, a sample size of 15 patients will provide 80% power to detect a 28% decrease in the HOMA-IR score (by a paired t-test analysis) at the P=0.05 level. This decrease in HOMA-IR score would be predicted to be associated with a clinically significant reduction in mortality.³³

9. Selected methods

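### The visit windows allow the pre-EMS assessment only 21 days after baseline, short of the stated 4-week optimization phase, and allow its 48-hour activity recording to run past the first EMS session

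*Combined protocol and SAP*

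**What the plan says.** Section C.1 (Overview) describes a run-in after enrollment: "Then all patients will undergo a 4-week care optimization phase", in which dialysis care is reviewed and adjusted towards the Table 1 goals. It then states: "Outcome markers will be reassessed again after completion of the 4-week care optimization phase". Section 8 gives the same order. It puts the second measurement after the 4 weeks of optimization and "before starting the EMS intervention, then at 8 and 16 weeks after initiation of the EMS" intervention.

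The visit schedule in Section 5 sets the days:

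- Section 5.1, Visit 1: "Baseline data collection (Day -35 to -28").
- Section 5.2, Visit 2: "Pre-EMS training data collection (Day -7 to 0").
- Section 5.3, Visit 3: "Initiate EMS training (Day 0").

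No text sets a minimum interval between Visits 1 and 2, or says that care adjustments are finished by Visit 2. Visit 2 includes DXA, the stress test for peak VO2, fasting blood and a 48-hour wrist activity recording worn between dialysis sessions. Sections 4.2.1 and 4.2.2 schedule peak VO2 and DXA three times only: before EMS and at 8 and 16 weeks. Current dialysis orders and concomitant medications are recorded again at Visits 9, 12 and 14, but Section 8 makes no use of them.

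**The concern.** The trial has one arm, so any EMS effect is read from change within patients. The run-in is there to let the effect of better dialysis care settle before the pre-EMS value is taken. If that value is taken before the phase is over, later care adjustments fall between the reference and the on-EMS measurements, and any effect they have is counted as change on EMS.

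Peak VO2 and DXA are the most exposed. Visit 2 is their only pre-EMS measurement, so no earlier value can show drift, and neither is repeated after EMS stops. HOMA-IR, LAR and the other five-point outcomes have a Visit 1 value and a post-EMS value as well, which help in reading a trend. Those values do not show a care change made between Visit 2 and Day 0.

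The other end of the window raises a separate, smaller problem. An activity recording labelled pre-EMS that starts on or just before Day 0 would include activity after the first EMS session. Section C.2 also has patients encouraged to be active outside the unit, which bears on this outcome.

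**Working it through.** **Inputs.** Visit 1 is Day -35 to -28 (Section 5.1). Visit 2 is Day -7 to 0 (Section 5.2). EMS starts on Day 0 (Section 5.3). The optimization phase is 4 weeks = 28 days (Section C.1). The activity recording takes 48 hours (Section 5.2).

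**The plan's own figure.** Gap = Visit 2 day minus Visit 1 day. Write Visit 1 as -35 + i and Visit 2 as -7 + j, with i and j each from 0 to 7. Then gap = 28 + j - i. Over the 8 x 8 = 64 day pairs the mean is 28, so the stated 4 weeks reproduces as the centre of the windows.

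**The range.**

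- Shortest: -7 - (-28) = 21 days.
- Longest: 0 - (-35) = 35 days.
- Pairs below 28 days: 28 of 64 (44%). Equal to 28: 8. Above 28: 28.

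These count calendar combinations. They do not give the probability that a patient has a short gap.

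**How much of the phase can be missed.** 28 - 21 = 7 days, and 7/28 = 25%. This is the single extreme pair, Day -28 with Day -7.

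**Does a full phase fit before EMS?** Visit 1 to Day 0 is 28 to 35 days, so yes, always. The fault lies in where Visit 2 may sit, and EMS does not start early.

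**Age of the laboratory values.** Section 5.2 accepts monthly labs drawn up to 7 days before what it calls the optimization visit. If that is Visit 2, the draw can be as early as -7 - 7 = Day -14. That is -14 - (-28) = 14 days after a Day -28 baseline.

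**The activity recording.** If it starts at Visit 2, it needs 2 days before the Day 0 session. A start on Day -2 just fits; a start on Day -1 or Day 0 does not. So 2 of the 8 days in the Visit 2 window cannot give a complete pre-EMS recording.

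**Both conditions together.** Visit 2 no later than about Day -2 and at least 28 days after Visit 1 puts Visit 1 no later than -2 - 28 = Day -30. The gap then runs from 28 to -2 - (-35) = 33 days. Narrowing the windows is not enough: Visit 1 at Day -35 to -30 with Visit 2 at Day -7 to -2 would still allow -7 - (-30) = 23 days, so the minimum must be written down.

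**The case against.** The windows need not be read alone. Section C.1 separately requires the phase to be complete, and 36 of the 64 day pairs (8 + 28) meet both texts. On that reading this is loose drafting around a correct intention. That is fair as to intent. Section 5 is nevertheless where the days are set, and it states no minimum.

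A reader might infer that EMS can precede the reference measurements generally. The documents do not support that. Visit 2 is titled as a pre-EMS visit, Section C.1 puts DXA before EMS, and Section 6.2 says "All patients will have a formal exercise stress test to determine" peak VO2 before EMS begins. Section 8 puts the primary and most secondary measurements before EMS too. For Day 0, what is missing is an explicit order of Visit 2 and Visit 3 procedures. Even for the activity monitor, stimulation is given only during dialysis, so none falls inside a recording worn between sessions. What can be recorded is activity after one session. HOMA-IR and LAR are not touched by this.

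Nor is the run-in the only safeguard. Section 4.1 plans a stratified analysis by achievement of care goals and correlations with training intensity. Sections 4.2.9 and 4.2.10 track anemia and mineral variables monthly, and Section 8 includes a measurement 4 weeks after EMS stops. These stand as partial protection. The stratification, however, is tied to a randomization that this trial does not have, and status at one time cannot identify later changes. Peak VO2 and DXA are left out of the post-EMS visit.

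Finally, care changes over 16 weeks of EMS are a longer exposure than one week before it, and a window change does not remove them. That also stands, and it is why the fix includes a listing.

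**Conclusion.** The schedule and the stated design do not agree. The pre-EMS assessment may come 21 to 35 days after baseline, although Sections C.1 and 8 place it after 4 weeks of optimization. Care changes in up to the last week before EMS can fall after the reference. The consequence is clearest for peak VO2 and DXA. For HOMA-IR and LAR it rests on taking the pre-EMS value as the reference, which Section 4.1 implies but does not state. Separately, a Visit 2 on Day -1 or Day 0 prevents the 48-hour recording from finishing before the first session, assuming that it starts at the visit.

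A reader might go further and conclude that part of the observed improvement in insulin resistance will be due to care. The documents do not allow that. They give no effect of Table 1 adjustments on HOMA-IR, LAR, peak VO2 or body composition, and no number of patients whose care would change late. The bias cannot be sized. In a pilot of up to 15 patients meant to estimate magnitude and variability, this is a modest inconsistency that is cheap to correct.

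**What to change.** - Reconcile the assessment windows in Sections 5.1 and 5.2 with Sections C.1 and 8: take Visit 2 measurements at least 28 days after Visit 1, and state this as a minimum interval.
- State that all Visit 2 measurements, including the 48-hour recording, are complete before the first EMS session.
- Shift the Visit 1 window to match. If the recording takes 48 hours and starts at Visit 2, Visit 1 falls no later than about Day -30.
- Add a by-patient listing of changes in dialysis orders and antidiabetic medication after Visit 2, from records already collected. This also covers changes in the days between a compliant Visit 2 and Day 0, and during EMS, which no window can exclude.
- Treat any analysis that omits patients with such changes as supportive only. It would select on events after the reference that EMS may itself cause: Section 4.2.10 expects that EMS may lower phosphate or reduce pill burden, and antidiabetic doses could fall if insulin resistance improves. With at most 15 patients, few might remain.

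The cost is slightly tighter scheduling before Day 0 and one listing. No new data are needed.

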2. Intervention. EMS is delivered to the quadriceps muscle groups using a neuromuscular electrical stimulator (using either the EMPI 300PV or its replacement, the Continuum device, EMPI, Inc). The device generates electrical impulses that are delivered to nerves stimulating the muscles through electrodes applied to the skin surface. Patients are taught how to place the adherent electrode pads over the quadriceps muscles on the upper thigh a few inches below the anterior iliac crest and just above the patella bilaterally. The electrodes will be applied at home or after coming to the dialysis unit just prior to each dialysis session. The patient's legs are extended straight on the reclining dialysis chair. The device is set to deliver biphasic electrical stimulation at 1-20 Hz and a pulse duration of 400 μ s applied for 1-12 seconds on and 1-12 seconds off. The stimulus intensity (typically 10-100 mA) is gradually increased to the maximum tolerable level for muscle contraction. The patient will feel contraction of the muscles and may feel mild shortness of breath and tingling of the skin but otherwise is expected to tolerate the stimulation well. The stimulation is delivered to one side for 15 minutes and then to the

opposite side for 15 minutes. This will be repeated at each dialysis session 3x/week. The first intervention will be observed through the entire treatment. If the patient feels excessively fatigued or other untoward signs the stimulator will be turned off until they feel better and then restarted to achieve the full treatment time.

At each study visit the study coordinator will confirm that the settings are correct and readjust the maximal tolerated stimulus intensity as needed to account for training. Patients will also be encouraged to be active and exercise as much as possible outside of the dialysis unit.

The total duration of the study for any patient is expected to be 6 months. We plan to complete the study of all patients within 2 years.

3. Study population.

Patients on hemodialysis three times a week at participating study sites within the UIHC dialysis program will be eligible to participate.

3.1 Inclusion & exclusion criteria.

Inclusion criteria include: age over 18 year old, able to provide informed consent, on maintenance hemodialysis for end stage renal disease and expected to stay in a participating dialysis unit for at least 6 months.

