4.2.11. Blood pressure and dialysis hypotension. Maintenance of blood pressure on dialysis can be a challenge for some patients, particularly those with large intra-dialytic fluid gains, and is associated with poor outcomes.⁶⁹ A prior study of EMS during hemodialysis found that EMS produced a statistically significant increase in BP and fewer hypotensive episodes compared to no EMS.²⁹ For the first EMS treatment in each patient we will directly record BP and pulse at 15-minute intervals before, during and after treatment with EMS. Thereafter, we will collect the BP and pulse data that is recorded (approximately every 15-30 minutes) as standard of care for every hemodialysis session. We will compare the average hemodialysis BP and pulse during the 4-week “care optimization” phase to that obtained during the EMS treatment and the 4-week post-EMS treatment phases to determine if EMS was associated with any change in BP or pulse. We will also analyze the frequency of dialysis sessions with a hypotensive episode (defined as SBP<90 mmHg or need for IV saline for hypotensive symptoms) during EMS compared to non-EMS treatment.

4.2.12. Muscle gene expression. Gene expression profiling of mRNA extracted from a skeletal muscle biopsy will be performed to give insight into the biological pathways activated by EMS both acutely and with chronic training in hemodialysis patients. Patients will be allowed to opt out of any of the muscle biopsy samples and still participate in the rest of the study. For these studies a muscle biopsy will be obtained as previously described⁷⁰ from the vastus lateralis muscle prior to the first EMS

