 - o Insulin and glucose
 - o Interleukin-6 (IL-6), tumor necrosis factor alpha (TNF α), C-reactive protein
 - o Glutathione (reduced and oxidized forms), glutathione peroxidase (GPx), superoxide dismutase (SOD), catalase (CAT), F2 isoprostane, protein thiols.
- Measure quadriceps muscle strength (bilaterally)
- 48 hour activity monitoring (using wrist watch monitor between dialysis sessions).

6. Patient risks.

6.1. Risk attributed to use of EMS device:

6.1.1. Muscle stimulation. Most patients will feel muscle contractions and perhaps some tingling of the skin but this should not be painful or harmful. There may be some muscle soreness initially as expected with new exercise but this should abate in a few days. The risks are minimal.

6.1.2 Muscular tetany. If EMS is misused it could cause muscular tetany leading to muscle pain and muscle breakdown (rhabdomyolysis). The stimulation intensity will be monitored so the risk will be minimal. Patients will have control of the EMS device to turn it off or decrease the stimulation intensity if it is causing pain. They will be monitored clinically for signs of excessive muscle pain and told to decrease the stimulus intensity or cut down the length of training as needed to prevent this complication.

6.1.3. Pacemaker or electrical stimulator complications. The electrical impulses generated by the EMS device might interfere with a cardiac pacemaker or other CNS/nerve stimulators. Patients with any implanted electrical device will be excluded from the study.

6.1.4. Electric shock. If the device is not properly maintained or defective then it could deliver an electric shock. This risk will be minimized by maintaining and using the device per manufacturer's instructions and have biomedical engineering check the device before use.

6.1.5. Skin burns. This is theoretically possible if the electrodes are kept in place and stimulated for prolonged periods of time. The risk is minimal in the current study since skin contact time is limited.

6.1.6. Skin bruising. Skin blood vessels may be damaged by the electrical stimulation and bruising could develop. The risk is minimal and will be monitored. EMS treatment parameters will be adjusted if this is clinically significant.

6.2. Risks attributable to increased exercise from EMS or exercise stress tests for VO₂ peak:

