A prior study of EMS during hemodialysis found that EMS produced a statistically significant increase in BP (SBP increased by 8 mmHg and DBP increased by 3 mmHg) while the device was turned on compared to when it was turned off.²⁹ Overall the average BP on dialysis was higher when people used EMS for 15 minutes out of every hour while on dialysis compared to no EMS (average BP = 125/66 with intermittent EMS compared to 121/64 when no EMS was performed). Fewer hypotensive episodes during a dialysis session were seen when patients used intermittent EMS compared to no EMS.

6.2.5. Fracture. Stress testing or EMS could lead to a bone fracture particularly in a patient with severe osteoporosis but this is considered unlikely to occur. EMS is also being studied as a mechanism to prevent osteoporosis.

6.2.5. Dizziness or confusion. Dizziness or confusion occurring during the exercise stress test or during an EMS training session is grounds for terminating the exercise and monitoring the patient until the symptoms resolve. The study physician will evaluate the circumstances of the event to decide whether further evaluation is needed and whether the patient can continue in the study.

6.2.6. Hypoglycemia. Low blood sugar with exercise might occur particularly in patients who are diabetic. If symptoms of hypoglycemia occur then the exercise will be terminated and sugar administered to the patient. A blood sugar will be measured and the study physician notified. This is unlikely to occur during EMS as the patient will be on hemodialysis, which provides glucose in the dialysate.

6.3. Risk of phlebotomy.

Phlebotomy may cause discomfort due to needle puncture, hematoma formation, blood loss, infection or syncope. It will be performed at the time of dialysis from your dialysis needle by trained personnel to limit risk.

6.4. Risk of radiation from a DXA scan.

A DXA scan delivers a dose of radiation that is approximately one tenth that of a standard chest X-ray and equivalent to the dose of radiation received during one-day exposure to natural background radiation.

6.5. Risk of taking health and depression assessment questionnaires.

Questions about personal health or depression might raise anxiety or concerns about personal health. If this occurs these will be addressed with the patient by a member of the study team or referred to their primary provider or social worker as appropriate.

6.6. Risk of a muscle biopsy under ultrasound guidance.

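### Section C.2 restarts EMS once a patient with untoward signs feels better, with no exception for the events for which Section 6.2 ends the session

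*Combined protocol and SAP*

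**What the plan says.** Section C.2 describes EMS as 15 minutes to one thigh and then 15 minutes to the other, at each dialysis session. For a patient who feels excessively fatigued or has "other untoward signs the stimulator will be turned off until they feel better and then restarted to achieve the full treatment time", it gives that single course of action. It does not define untoward signs, list exceptions or mention Section 6.

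Section 6.2 states that it gives the management of problems seen with stress testing or EMS training. Three of its items name EMS sessions:

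- Section 6.2.5 (the second of two items with that number): "Dizziness or confusion occurring during the exercise stress test or during an EMS training session is grounds for terminating the exercise". The patient is monitored until the symptoms resolve. Then "The study physician will evaluate the circumstances of the event to decide whether further evaluation is needed", and whether the patient can stay in the study.
- Section 6.2.4: "An EMS session will be terminated for a systolic BP<90".
- Section 6.2.3: "An EMS session will be terminated for a systolic BP>200 or diastolic BP>110".

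On monitoring, Section 4.2.11 relies on blood pressure and pulse "recorded (approximately every 15-30 minutes) as standard of care for every hemodialysis session". At the first EMS treatment only, they are recorded every 15 minutes before, during and after.

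**The concern.** The stopping rules exist. The difficulty is that the section describing how treatment is delivered states a different rule for an overlapping set of events and does not defer to them. Dizziness is an untoward sign on any ordinary reading. Someone following C.2 would wait for it to pass and then complete the session. Someone following Section 6.2.5 would have grounds to end the session and would bring in the study physician.

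What is at stake is patient safety at the chairside: a patient could be stimulated again after an event that the protocol itself treats as a reason to stop. Section 4.2.11 notes that maintaining blood pressure on dialysis is difficult for some patients, so symptomatic hypotension is foreseeable here.

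**Working it through.** No arithmetic settles this, because it is a comparison of rules. The table follows the same event through both sections.

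| Event during EMS | Section C.2 | Section 6.2 | Conflict? |
|---|---|---|---|
| Dizziness or confusion that resolves | Off, wait until better, restart to full time | Grounds to terminate; monitor; study physician evaluates (6.2.5) | Yes, directly |
| SBP<90 with symptoms that resolve | Same | Session terminated (6.2.4) | Yes, secondarily |
| SBP>200 or DBP>110 with symptoms that resolve | Same | Session terminated (6.2.3) | Yes, secondarily |
| Any of these pressures without symptoms | Trigger not clearly met, since C.2 turns on how the patient feels | Session terminated | Not claimed |
| Fatigue or minor discomfort only | Same | No termination rule | No |

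1. **Dizziness or confusion.** Section 6.2.5 names the EMS session, so nothing needs to be inferred about its scope. It differs from C.2 in two ways: termination instead of a pause, and a physician evaluation that C.2 omits.

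2. **Blood pressure.** Sections 6.2.3 and 6.2.4 set numeric limits that apply whatever the patient feels. They meet C.2 only when the breach is also symptomatic. C.2 then restarts on feeling better and asks for no new reading. The limits still apply after a restart, so a pressure still out of range would end the session at the next measurement. The physician steps in these two items are attached to the stress test, so for EMS the difference is only termination against restart.

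3. **Whether a routine reading would fall before the restart.** An uninterrupted treatment lasts 2 × 15 = 30 minutes. At one reading every 15 to 30 minutes, that gives about 30/30 = 1 to 30/15 = 2 readings. A reading between symptom relief and restart is possible but not assured.

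4. **Precedence.** No text says that Section 6 overrides C.2 or the reverse.

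**The case against.** The strongest reply is that ordinary reading reconciles the two sections. C.2 is a general account of the intervention and Section 6.2 presents itself as the management section, so its specific rules should prevail. The C.2 phrase also follows a description of expected mild sensations and is paired with fatigue, which suggests tolerability rather than a medical event. And it comes straight after a sentence about observing the first treatment, so it may concern that session alone, when blood pressure is recorded every 15 minutes.

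These readings are plausible, and the drafters may have intended one of them. The text states none of them, and those at the chair should not have to infer a safety rule. If C.2 covers only the first session, the conflict remains for that session. It is also fair that grounds for termination leave some discretion in Section 6.2.5. The physician's evaluation there is not worded as optional, and the blood pressure rules are unconditional.

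The safeguards stand and lower the risk: patients control the device (6.1.2), a stress test with a physician available precedes EMS (6.2), unstable angina and SBP>170 are exclusions (3.1), and an independent monitor reviews safety every 3 months (7). None of them says which rule applies.

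A reader might infer two stronger points, and the documents support neither:

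- *Every item in Section 6 collides with C.2.* The arrhythmia termination rule (6.2.2) names only the stress test. Angina (6.2.1) and hypoglycemia (6.2.6) reach EMS only through the general word exercise and the Section 6.2 lead-in, and 6.2.6 calls hypoglycemia unlikely during EMS. Section 6.1.2 has patients watched for "signs of excessive muscle pain and told to decrease the stimulus intensity or cut down the length of training as needed"; that is a specific allowance which can sit beside a general target of full time.
- *Wrong restarts would be common because most sessions have no study visit.* Counting such sessions does not measure how often the rules collide. Sections A and B describe a supervised setting with dialysis unit staff.

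**Conclusion.** The inconsistency is real and worth correcting, at low magnitude. There is one direct conflict (dizziness or confusion, 6.2.5) and a secondary one for symptomatic breaches of the blood pressure limits in 6.2.3 and 6.2.4. Followed literally, C.2 restarts a patient whom Section 6.2 stops.

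The conclusion rests on two readings: that untoward signs include dizziness, confusion and symptoms of abnormal blood pressure, and that without a precedence statement both sections apply. The number of affected sessions cannot be estimated, because the documents give no event rate. No endpoint, sample size or analysis is affected. A reader might infer that the protocol lacks stopping rules for EMS; it has them, and what is missing is their link to C.2.

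**What to change.** In Section C.2, limit the restart to fatigue or minor discomfort and add an exception along these lines: *except for events for which Section 6.2 terminates the EMS session (dizziness or confusion, SBP<90, SBP>200 or DBP>110); that session is not restarted, and any physician evaluation required by 6.2 is completed before EMS resumes.*

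Cover the same rule in the device training already planned at Visit 3 (Section 5.3).

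The cost is one sentence in an amendment and one training point, with no added visits or procedures. A few sessions will be incomplete, which Section 6.2 already implies.
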